- Exclusion criteria: Respondents will be excluded if they are pregnant or are planning on becoming pregnant during the study; have difficulty using tampons; currently have, or have had TSS; currently have an STI; currently have a UTI; are currently using current antibiotics, or used antibiotics within 4 weeks prior to enrollment; are currently using current antifungals, or used antifungals within 4 weeks prior to enrollment; or have an autoimmune condition.

Study Design

- This study will be a longitudinal, interventional, case-crossover study with three exposure levels:
 - Experimental exposure levels: Each subject will use Tampax® Pearl® Regular Tampons and Playtex® Gentle Glide® 360°® Regular Tampons for one menstrual cycle each, in a randomly assigned order.
 - Control exposure level: Each subject will use menstrual products according to their normal habits for a third menstrual cycle.
 - A case-crossover design ensures exchangeability between treatment windows within each subject for all time invariant characteristics. Under exchangeability and the assumptions of an intent-to-treat analysis (covered in Methods – Whole Community Analysis &

Statistics), the actual outcome observed under one treatment for an individual equals the counterfactual outcome under that treatment for that individual, so association between expanded tampon shape and VMB composition represents a causal relationship. This study design and the intent-to-treat analytic strategy will allow us to make causal inference in reference to the effect of expanded tampon shape on VMB composition.

- Vaginal swabs will be self-collected by each subject twice weekly for four different exposure windows (Fig. 1):
 - A 2-3 week baseline window after the last menstrual period prior to enrollment; 4-6 baseline samples per subject.
 - One menstrual cycle using the Tampax® Pearl® Regular Tampons; 8 samples.
 - One menstrual cycle using Playtex® Gentle Glide® 360°® Regular Tampons; 8 samples.
 - The final menstrual cycle with menstrual product use according to the subject's normal habits; 8 samples for the subject's normal habits.

[figure not shown]

Figure 1: Study design.

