- Covariate data collection with each swab: We will provide a short survey with each swab on which subjects will record whether the swab was collected during menses as well as any changes in sexual activity, hygiene, medication use, general health, vaginal health, contraception use, pregnancy, menses since the baseline study or prior swab.
- We will remind subjects to collect swabs with twice-weekly text messages, emails, or phone calls based on preference.

Whole Community Analysis & Statistics

- DNA will be isolated from vaginal swab samples using a PowerMag Soil DNA isolation kit (Mo Bio Laboratories, Inc.) and an epMotion robot (Eppendorf epMotion 5075). The DNA samples will be submitted to the University of Michigan

Center for Microbial Systems Laboratory for amplification and sequencing of the V4 region of the 16S rRNA gene. The V4 region of the bacterial 16S rRNA gene will be amplified using dual-indexing sequencing strategy and sequenced on the Illumina MiSeq platform as described by Kozich et al. and Seekatz et al. After sequencing is completed, the 16S rRNA gene sequences will be processed and analyzed using the mothur software (version 1.34.3) and MiSeq SOP (http://www.mothur.org/wiki/MiSeq_SOP). Following sequence processing and alignment to the SILVA reference alignment [Preusse 2007], sequences will be binned into operational taxonomic units (OTUs) of 97% sequence identity. In our preliminary studies, we were able to detect and distinguish 6 different types of *Lactobacillus* among the top OTUs (>2% in at least 1 sample) from vaginal swab samples using an OTU definition of 3% sequence difference with sequences from the V4 region of the 16S rRNA gene. Relative abundances of OTUs will be calculated and we will test the dependence of within subject θ_{YC} distances on expanded tampon shape using Mann-Whitney tests or Kruskal-Wallis test, as dictated by the number of comparisons. Principal components analysis (PCoA) will be used to visualize θ_{YC} distances between samples within subjects. The same analysis protocol was used in our previous studies (HUM00098494, HUM00086661).

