- Intent to treat analysis: This analytic strategy assumes each subject's actual exposure is exactly as it was assigned (complete compliance with assigned interventions, exposure fixed for each subject during each treatment window, complete follow-up). The implications of this analytic approach in conjunction with the within-subject exchangeability produced by the case-crossover design (covered in Method – Study Design section) is that the actual outcome observed under one treatment for a subject equals the counterfactual outcome under that treatment for that subject, so association between expanded tampon shape and VMB composition represents a causal relationship. This study design and analytic strategy will allow us to make causal inference in reference to the effect of expanded tampon shape on VMB composition.

Benefits

- This study will help to provide information on whether the use of tampons is associated with changes in the VMB over the course of a menstrual cycle. If there are associated changes in the VMB associated with tampon use then our research could help provide information on a potentially modifiable time point to help improve the vaginal health of women.

Risks

- No more than minimal risk
 - Discomfort with tampon use - rare - we are recruiting women that are currently tampon users.
 - Toxic shock syndrome (TSS) - rare- the rates of TSS with currently available tampons are extremely low. Each women will be given manufacturers instructions which include ways to decrease the risk of TSS.

- Discomfort with vaginal swab collection - rare- the Starplex swabs have been used in numerous trials by our lab without any problems given that the swab is considerably smaller than the size of the tampon introducer. Additionally, detailed instructions on sample collection are provided.
- Disclosure of subject information - rare- each subject will be provided a unique ID for the data collected (samples and surveys). All collected information will be maintained in a password protected lab file manager.
- All recruited women in this trial will be active tampon users and thus we do not foresee any likelihood of these risks interfering with the subjects day to day living.

Incentives

- Each subject will receive a \$20 gift card for participating in this study.

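### The causal claim for tampon shape rests on a misdefined intent-to-treat analysis and on case-crossover exchangeability instead of the randomised order; sequence balance, period and carry-over handling are not stated

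*Combined protocol and SAP*

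**What the plan says.** Under Study Design, each woman uses the two study tampons "for one menstrual cycle each, in a randomly assigned order". A third cycle with her usual products follows. The causal argument in the same section starts from the statement that "A case-crossover design ensures exchangeability between treatment windows within each subject for all time invariant characteristics". It adds the assumptions of an intent-to-treat analysis and concludes "so association between expanded tampon shape and VMB composition represents a causal relationship".

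The intent-to-treat item under Whole Community Analysis & Statistics says that this strategy assumes each woman's "actual exposure is exactly as it was assigned (complete compliance with assigned interventions, exposure fixed for each subject during each treatment window, complete follow-up". It takes this "in conjunction with the within-subject exchangeability produced by the case-crossover design" and ends by saying that design and analysis "will allow us to make causal inference in reference to the effect of expanded tampon shape on VMB composition".

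The only product comparison with a named test is in the same section. The plan will test the dependence of within-subject θYC "distances on expanded tampon shape using Mann-Whitney tests or Kruskal-Wallis test, as dictated by the number of comparisons". The text gives no period or sequence term, no numbers per sequence and no assumption about carry-over.

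Under Outcomes and aims, the shape comparisons are exploratory. Hypotheses 2.1 and 2.2 expect changes seen during menses to persist between menses.

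**The concern.** What is described is a randomised two-period crossover followed by a fixed third cycle. Its causal strength comes from the random order, and neither causal passage uses that order as a premise.

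The two premises that are used do not carry the conclusion. Exchangeability on time-invariant characteristics does not cover change from one cycle to the next. Intent to treat is analysis by assignment regardless of use; it neither requires nor provides full compliance. As written, it gives no rule for a woman who uses another product or misses swabs.

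The features that a crossover comparison depends on are also missing: balance of the two sequences, allowance for a cycle effect, and a position on carry-over. A real difference could be missed because an unmodelled cycle effect inflates the noise. At an uneven split, part of the cycle effect would appear as a product effect.

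**Working it through.** The documents give no alpha, power, SD, cycle effect or randomisation method, so there is no design figure to reproduce.

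**Inputs.** From the documents: 20 women enrolled (Recruitment also speaks of recruiting 40), two consecutive product cycles, random order. Assumed: simple 1:1 randomisation, two-sided 5%, normal data. Unless stated otherwise, effects are in SDs of the within-woman difference between cycles.

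**1. Chance imbalance.** With X ~ Binomial(20, 0.5):
- exactly 10:10: C(20,10)/2^20 = 0.176
- 12:8 or worse: 2·P(X ≥ 12) = 0.503
- 14:6 or worse: 2·P(X ≥ 14) = 0.115

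**2. What an unadjusted difference keeps.** Let τ be the product effect (A minus B), π the cycle-2 effect, and λA and λB the carry-over from each product. Women in order AB give A − B = τ − π − λA. Women in order BA give τ + π + λB. The crude mean therefore contains π(nBA − nAB)/20. That is 0 at 10:10, −0.2π at 12:8 and −0.4π at 14:6. The average of the two sequence means removes π at any split.

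**3. False-positive rate, no product effect (simulation).**
- Order by fair coin, unadjusted signed-rank test: 4.6% and 5.1% at π = 0.5 and 1. The overall level is kept.
- Exactly 14:6, π = 1: signed-rank about 15 to 17%; Mann-Whitney on cycle 1 minus cycle 2 differences between sequences about 4%.
- Exactly 14:6, unpaired Mann-Whitney, π equal to 1 SD of a single cycle's value: about 15%, 9% and 4.5% at within-woman correlations of 0.3, 0.6 and 0.8.
- The same test with π equal to 1 SD of the within-woman difference: 18.6%, 7.6% and 1.2%. The scales differ because the SD of the difference is √(2(1 − ρ)) = 1.18, 0.89 and 0.63 single-cycle SDs at these correlations.

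**4. Power at 10:10 (simulation).** The product effect is 0.66 SD, which a paired t-test on 20 women detects with 80% power.

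| Cycle effect (SD) | Signed-rank, unadjusted | Mann-Whitney between sequences |
|---|---|---|
| 0 | about 0.77 | about 0.75 |
| 0.5 | about 0.70 | about 0.75 |
| 1 | about 0.43 | about 0.75 |

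**5. Carry-over.** From step 2, the period-adjusted estimate is τ − (λA − λB)/2, so differential carry-over d = λA − λB shifts it by d/2. Equal carry-over cancels. If only A carries over, at 25% or 50% of a true τ = 1, the estimate is 1 − 0.25/2 = 0.875 or 1 − 0.50/2 = 0.75. That is attenuation, not a false effect.

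**6. Can distance to baseline replace the θYC comparison?** Simulated case: three taxa, with A raising one minor taxon and B raising another by the same amount. Mean A-to-B θYC was 0.54, against 0.21 within a cycle. Mean distance to baseline was 0.36 for both products. A period-adjusted test of distance to baseline rejected only about 4%. It measures the size of a shift but not its direction, and Hypothesis 1 predicts growth of different taxa.

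**The case against.** The random order is stated in the same section as the causal argument, and *this study design* can be read to include it. Figure 1 is not shown and may depict the sequences. The sentence on time-invariant characteristics is correct as far as it goes. This stands: randomisation is not absent, and a reader who infers that the trial cannot support a causal comparison of the two products goes too far. The fault is that the written argument does not use what supports it.

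A reader might also infer that the planned tests are invalid. They are not, on average: random order holds the level near 5%. The inflation in step 3 is conditional on an uneven split and on an assumed cycle effect. It also depends on the form of the test and the correlation, and for the unpaired Mann-Whitney it can disappear.

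A third tempting reading is that carry-over would produce a false shape effect. With no product effect and d = 0.5 or 1 SD, the adjusted test does reject 16% or 50%. But the plan's hypotheses concern persistence of changes caused by shape, so without such an effect there is little to carry over unequally. Cycles of 21 to 35 days also separate the exposures, and swabs between menses measure persistence. What remains is that the assumption is unstated.

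Compliance does matter for reading the contrast as an effect of actual use. It should be stated as a separate condition, not as the meaning of intent to treat.

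Three further inferences are not supported. Complete follow-up need not mean that every swab is returned; the plan does not say so. The per-swab survey will "record whether the swab was collected during menses as well as any changes in sexual activity, hygiene, medication use, general health, vaginal health" and further items. Product used is not named, but the form is not in the documents. The usual-products cycle is third for every woman, but the plan's causal conclusion concerns shape, not that contrast.

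**Conclusion.** The concern holds in this form. Intent to treat is misdefined, the causal conclusion does not rest on the randomised order, and sequence balance, period adjustment and carry-over are not addressed.

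The cost is mainly power: at an even split, a cycle effect of 0.5 or 1 SD lowers signed-rank power by about 0.07 or 0.34 (0.77 − 0.70; 0.77 − 0.43). At an uneven split the estimate is also distorted, by 0.4 of the cycle effect at 14:6. These sizes rest on assumed cycle effects and simple randomisation.

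Even with the argument repaired, the randomised contrast identifies the effect of the assigned product. Attribution to shape also requires that the differences in material and string listed under Menstrual Products do not matter, and that the assigned product was used.

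Because the shape aims are exploratory, this should be fixed but is not critical.

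**What to change.** 1. Allocate the two sequences 1:1 from a balanced list (10:10 for 20 women).
2. Replace the intent-to-treat text with: *all randomised women analysed by assigned product regardless of product used, using all available swabs*. Rest the causal claim on the randomised order plus a stated assumption of no differential carry-over. State the two further assumptions needed to move from assigned product to shape.
3. For change from baseline in *Lactobacillus* abundance, compare cycle 1 minus cycle 2 differences between the two sequences, one value per woman. Mean θYC distance to baseline may be tested the same way, as a measure of size of shift only.
4. Keep a direct A-versus-B θYC comparison for Hypothesis 1, tested by re-randomising the sequence labels across women. The statistic must depend on the labels. A woman's own cycle 1 to cycle 2 distance is unchanged when they are swapped, so use, for example, distances between samples of different women under different products against those under the same product.
5. Use the between-menses swabs already planned to report return to baseline before the second product. With six days of menses and a swab every 3.5 days, a 28-day cycle gives (28 − 6)/3.5, about 6. Compare their θYC distance to baseline with the woman's own baseline-to-baseline distances (6 to 15 pairs from 4 to 6 swabs).

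Optional: a collection-day question on the product used, and a non-randomised label on comparisons with the third cycle.

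The cost is wording, an allocation list and slightly more analysis of data already planned. If there is no cycle effect, power falls slightly (about 0.75 against 0.77).

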Examining the Impact of Tampon Use on the Vaginal Microbiota

NCT03346759

March 29, 2018

Tampon Study Proposal

Abstract

To date, a great deal of work has been done to characterize the composition of the vaginal microbiota (VMB) in women of reproductive age. While several different community types have been identified, it is widely accepted that communities dominated by *Lactobacillus* spp confer colonization resistance, and thus protect against bacterial vaginosis (BV), STI, and other urogenital infectious diseases [Hickey 2012]. Conversely, mixed communities that often include *Gardnerella vaginalis*, *Prevotella* spp., *Mycoplasma* spp., and/or Gram-positive cocci and relatively few *Lactobacillus* spp are considered unhealthy states and may contribute to BV and various sequelae including infertility, endometriosis, pelvic inflammatory disease, and increased risk of STI [Hickey 2012]. Considering both the relationship between VMB composition and reproductive health, and the high prevalence of tampon use, which, for many women, occurs at regular intervals for the duration of their reproductive life, it is surprising how few studies have examined the effect of tampon use on VMB composition. Moreover, the majority of these studies are limited by the use of culture-dependent methods focused on the presence/absence of a small number of species (*Lactobacillus* spp, *Staphylococcus aureus*, *E. coli*, group B *Streptococcus*, and/or *Gardnerella vaginalis*) [Onderdonk 1986, Onderdonk 1987, Chow 1989, Shehin 2003, Chase 2007, Chase 2010, Hochwalt 2010]. The one study to date that has used culture-independent VMB community analysis in response to tampon use was limited by its sample size of 7 women. Further, the investigators only collected vaginal swabs at two points during each menstrual cycle [Hickey 2013]. The conflicting findings of these studies make this an even more compelling research question. In order to address this striking knowledge gap, we propose a longitudinal, interventional, case-crossover study design to examine whether expanded tampon shape affects VMB composition during, and in between menses. We will recruit 20 women from the University of Michigan, Ann Arbor to use Tampax® Pearl® Regular Tampons (expand into a rectangular prism-like shape) and Playtex® Gentle Glide® 360°® Regular Tampons (expand into a conical shape) for one menstrual cycle each, in a randomly assigned order. We will obtain twice-weekly self-collected vaginal swabs for a 2-3 week baseline window before the first menstrual cycle with an assigned tampon, followed by the two menstrual cycles with assigned tampon use, and finishing with one menstrual cycle with menstrual product use according to each subject's normal habits. DNA will be isolated from the vaginal swabs, and the bacterial 16S rRNA encoding genes will be amplified by PCR. Sequencing will be performed using the MiSeq Illumina platform, and analyzed to answer the above questions. We hypothesize that VMB composition will vary between menses using the Tampax® Pearl® Regular Tampons and Playtex® Gentle Glide® 360°® Regular Tampons, and that persistence of these VMB changes will vary based on baseline VMB community type.

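### The assigned cycles can support a Tampax versus Playtex product contrast, not the causal effect of expanded tampon shape that the protocol claims

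*Combined protocol and SAP*

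**What the plan says.** The Abstract and the end of the Background give the aim as a study "to examine whether expanded tampon shape affects VMB composition during, and in between menses". Under Study Design, the experimental exposure levels are two named products, Tampax Pearl Regular and Playtex Gentle Glide 360 Regular, used "for one menstrual cycle each, in a randomly assigned order". The same section says that the design "ensures exchangeability between treatment windows within each subject for all time invariant characteristics". It combines this with the intent-to-treat assumptions and concludes: "so association between expanded tampon shape and VMB composition represents a causal relationship".

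The intent-to-treat paragraph under Whole Community Analysis & Statistics repeats the conclusion, saying that the investigators will be able to "make causal inference in reference to the effect of expanded tampon shape on VMB composition". Its listed assumptions are "complete compliance with assigned interventions, exposure fixed for each subject during each treatment window, complete follow-up". The planned test in that section is of within-subject θYC "distances on expanded tampon shape using Mann-Whitney tests or Kruskal-Wallis test".

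The two exploratory aims and Hypotheses 2.1 and 2.2 also speak of changes caused by a change of shape. Hypothesis 1 is worded differently: it contrasts the two products and offers shape as the reason. The primary and secondary outcomes do not mention shape.

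**The concern.** What was randomised and what is claimed are different things. A woman is assigned to a product in each of two cycles, and the product brings its shape, string, materials and brand together. Exchangeability over the woman's own fixed characteristics makes her a fair comparison with herself. It says nothing about which feature of the product produced a difference. Intent-to-treat does not help either, because it concerns adherence to the assigned product and not the separation of that product's attributes.

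At stake is the headline interpretation. Shape is in the objective sentence and is the named target of both causal statements. A difference between the assigned cycles would be reported as a causal effect of shape, when the design can attribute it only to the product as a whole. The converse also applies: a null product contrast would not by itself show that shape has no effect.

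**Working it through.** The plan gives no figure on this point to reproduce. The check is one of identifiability, followed by a comparison of two parts of the Menstrual Products section.

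**1. What the two assigned cycles can estimate**

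Inputs: 20 women (Abstract, Background), 2 assigned cycles each, and 2 products with one product per shape (Study Design, Menstrual Products). The protocol does not state how the two orders are split; an equal split was assumed. The aliasing in the last two rows of the table does not depend on the split.

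Subject-cycles: 20 × 2 = 40. A linear model was set up with one indicator per woman, a period term, and then product-level attributes coded by product.

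| Terms | Columns | Rank |
|---|---|---|
| Woman + period | 20 + 1 = 21 | 21 |
| Woman + period + product | 22 | 22 |
| Woman + period + shape + material | 23 | 22 |
| Woman + period + shape + material + string | 24 | 22 |

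One product-level contrast is estimable (22 − 21 = 1). Each further attribute adds a column identical to the product column, so the rank stays at 22. The result is general: with n women, the rank is n + 2 however many attributes are named. More women lengthen the identical columns without making them differ, and more swabs per cycle only repeat rows. The planned rank tests face the same limit, because shape and product define the same grouping.

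**2. Whether the third cycle helps**

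The control level is described thus: "Each subject will use menstrual products according to their normal habits for a third menstrual cycle". Those products are self-chosen and outside the randomised order, and the cycle comes last for everyone. It adds no randomised contrast that could separate shape from the rest of the product.

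**3. Whether the protocol's own defence closes the gap**

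The justification for the two tampons calls shape the primary structural difference. Two of its supporting statements do not carry the weight placed on them.

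- *Material.* The justification describes both tampons as a blend of cotton and rayon. The listing for Tampon B (Playtex) gives rayon fibre and polyester for the tampon, and cotton only for the string. Counting the string as part of a blend would still leave out the listed polyester. For Tampon A (Tampax), the listing allows cotton, rayon or both in the core, which is compatible with a blend but does not establish one. The clear conflict is therefore for Playtex.
- *String.* The justification names the string as a further substantial difference: braided for Tampax, straight and two-strand for Playtex. It reports that the braid holds up to 12 extra drops of fluid. It then sets the string aside because the string touches little epithelium. Yet its pathway for shape runs from contact area to greater absorption of menses, and the string's fluid capacity bears on absorption. The capacity is mentioned but not answered.

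**4. Conditions for the product contrast itself**

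Even the product contrast needs the first assigned cycle not to carry over into the second. Hypothesis 2.1 expects changes to persist between menses, for longer in some women than in others. The assumptions listed in the intent-to-treat paragraph do not include this condition.

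**The case against.** The best reply is that the protocol saw the problem. It chose two products with plastic applicators, argued that shape is the main difference, disclosed the string and its capacity, and gave a reason for discounting it. That reason is not arbitrary, since the proposed shape pathway begins with contact area. Product wording is also plentiful: the Abstract's closing hypothesis, Hypothesis 1, the definition of the experimental levels and the tampon justification all name products or brands. The third cycle is already described as usual-habit use outside the randomised order. A reader can see what was assigned.

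Most of this stands, and it confines the fault to the inferential label; nothing about the assignment is hidden. It does not rescue the label. An argument that other differences are unlikely to matter is an assumption brought to the data, whereas the causal statements present the shape reading as following from the design and analysis. Part of that argument also rests on the contradicted material statement.

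Two stronger readings are tempting. A reader might infer that the string's capacity offsets the shape effect by some calculable amount. The documents give no figure for the absorption attributed to shape, and they do not say that fluid held in the string alters vaginal growth conditions, so neither the size nor the existence of an offset can be shown. A reader might also count the Tampax cover fabric or the layering named in a Playtex figure caption as further confounders. The figure is not available, and the listings may differ only in detail, so the documents do not establish these as real differences.

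**Conclusion.** Wrong as written, in the causal statements and wherever shape is named as the randomised contrast. The design yields one randomised product contrast. Shape is fully aliased with every other attribute on which the two products differ, and sample size is no remedy. Reading the contrast as a shape effect needs the untested assumption that no other product difference affects the vaginal microbiota. The product contrast itself needs no carryover between the assigned cycles, as well as the compliance and follow-up conditions already listed. The Playtex material conflict stands on the text.

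No bias can be sized from the documents, and none is asserted. A reader might infer that the crossover is invalid or that the main endpoints are compromised. Neither follows from this point: the product comparison remains worthwhile, and the primary and secondary outcomes do not refer to shape.

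**What to change.** - In the causal statements (Study Design and the intent-to-treat paragraph), the objective sentence (Abstract and Background), both exploratory aims, Hypotheses 2.1 and 2.2, and the planned test, name the contrast as assigned product: Tampax Pearl Regular versus Playtex Gentle Glide 360 Regular. Present shape as a hypothesised mechanism, as Hypothesis 1 already does.
- Beside the causal statements, say that a shape interpretation assumes no other product difference matters and that this is not tested. Add absence of carryover between the two assigned cycles to the listed assumptions.
- In Menstrual Products, reconcile the Playtex material listing with the justification, and address the string's reported fluid capacity as well as its contact with the epithelium.

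This is a change of wording only: assignment, sample size, endpoints and tests stay as they are. The cost is that the study could no longer claim a causal effect of shape.
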